Appendix 1. List of recruiting centers.

Dipartimento Area Materno - Infatile

SC NEFROLOGIA E DIALISI PEDIATRICA – TRAPIANTI DI RENE – Direttore: [name]

[contact]

email: [contact]

1. Schedule of assessments

A. Schedule of assessments: main population (incident INS)

	Enrolment (Onset)	6-weeks visit (End of metil- prednisolone pulses*)	6-months visit	12-months visit	First relapse
Informed consent	x				
Inclusion/exclusion criteria	x				
Demographic data	x				
Physical examination	x	x	x	x	x
Assessment of oedema	x	x		x	x
Medical history	x			x	
Vitals sign ¹	x	x	x	x	x
Clinical blood sample ²	x	x	x	x	x
Clinical urine sample ³	x	x	x	x	x
Blood for genetic analysis	x				
Blood for mononuclear cells analysis	x	x		x	x
Urine for molecular analysis	x	x	x	x	x
Serum for molecular analysis	x	x	x	x	x

¹ Height, weight, blood pressure

² BUN, sCr, albumin, Na, K, total cholesterol, IgG, triglycerides, (local laboratory) serum complement C3 (local laboratory, only at enrolment)

Dipartimento Area Materno - Infatile

SC NEFROLOGIA E DIALISI PEDIATRICA – TRAPIANTI DI RENE – Direttore: [name]

[contact]

email: [contact]

³ Urine protein/creatinine ratio, urinalysis (local laboratory)

* Only in patients not achieving remission at week 4

B. Schedule of assessments: control group

	Enrolment
Informed consent	x
Inclusion/exclusion criteria	x
Demographic data	x
Physical examination	x
Vitals sign ¹	x
Clinical blood sample ²	x
Clinical urine sample ³	x
Blood for PBMC extraction	x
Urine	x
Serum	x

¹ Height, weight, blood pressure

² BUN, sCr, albumin, Na, K, total cholesterol, triglycerides, IgG, IgM, IgA (at local site)

³ urine protein/creatinine ratio, urinalysis (at local site)

Dipartimento Area Materno - Infatile

SC NEFROLOGIA E DIALISI PEDIATRICA – TRAPIANTI DI RENE – Direttore: [name]

[contact]

email: [contact]

C. Schedule of assessments: validation cohort (prevalent INS)

	Enrolment (Relapse)	Remission
Informed consent	x	
Inclusion/exclusion criteria	x	
Demographic data	x	
Physical examination	x	x
Assessment of oedema	x	x
Medical history	x	
Vitals sign ¹	x	x
Clinical blood sample ²	x	x
Clinical urine sample ³	x	x
Blood for PBMC extraction	x	x
Urine	x	x
Serum	x	x

¹ Height, weight, blood pressure

² BUN, sCr, albumin, Na, K, total cholesterol, triglycerides, IgG, IgM, IgA (at local site)

³ urine protein/creatinine ratio, urinalysis (at local site)

Dipartimento Area Materno - Infatile

SC NEFROLOGIA E DIALISI PEDIATRICA – TRAPIANTI DI RENE – Direttore: [name]

Medical University Gdansk	Rare Diseases Centre and Department of Biology and Medical Genetics	[name]	Biological sample processing, exome sequencing analysis
University of Istanbul	Division of Pediatric Nephrology.	[name]	Patients recruitment, biological sample processing, epigenetics analysis
Vilnius University Faculty of Medicine	Clinic of Children's Diseases	[name]	Patients recruitment and bioinformatic analysis

External services

Name	Type of service
University of Torino, [name]	EV data analysis

Dipartimento Area Materno - Infatile

SC NEFROLOGIA E DIALISI PEDIATRICA – TRAPIANTI DI RENE – Direttore: [name]

[contact]

email: [contact]

Eurofins, Italy	Novaseq 6000
MacroGen UE	Sample shipping and exome sequencing

4. Amendments

Not applicable.

5. Timelines

Stato dello studio	Pianificazione
Inizio della raccolta dati	30/10/2024
Fine della raccolta dati	30/10/2027
Report finale dello studio	30/03/2028

Dipartimento Area Materno - Infatile

SC NEFROLOGIA E DIALISI PEDIATRICA – TRAPIANTI DI RENE – Direttore: [name]

[contact]

email: [contact]

6. Rationale and background

Idiopathic nephrotic syndrome (INS) is the most common glomerular disease in children, with an annual incidence of 2-7 cases per 100,000 children. INS is characterized by proteinuria, edema, hypoalbuminemia, hyperlipidemia, and thrombotic complications (1). The disease has an extremely variable clinical behavior, and the first-line treatment is based mainly on steroids and other immunosuppressive (IS) drugs. The response to steroids guides the actual classification. Approximately 80–90% of patients with nephrotic syndrome are initially steroid sensitive (SSNS), while 10–20% will not achieve remission despite second or third-line treatments and are defined as steroid resistant (SRNS) (2). The SSNS population exhibits an uncertain clinical course, characterized by various relapses and requiring immunosuppressive treatment, prolonged into adulthood in 1/3 of patients. These treatments have major side effects and come with an increased socio-economic burden as seen all over Europe.

There is no biomarker able to predict the INS clinical course (response to treatment and occurrence of relapses) and to tailor the treatment for most patients. INS, at least in the steroid-sensitive forms, shows an immune pathogenesis. Potential causative circulating factors have been described, however none has been unequivocally shown to be pathogenic. The recent identification of genetic risk loci associated with HLA Class II region among the most represented in SSNS patients (3) emphasizes the central role of adaptive immunity in the NS pathogenesis. From the cellular side, various experimental evidence implies that dysfunction in some populations of T lymphocytes may be related to the pathogenesis of the disease (4). Among these, a Th17/Treg imbalance has been described in patients with minimal change glomerulopathy (5). Furthermore, the remission after the use of Rituximab, a monoclonal antibody against the CD20 surface antigen, suggests that B cells may also be involved in the pathophysiology of NS (6). The role of autoantibodies as circulating permeability factors able to directly damage the glomerular barrier, leading to proteinuria in INS, has been recently explored. Antibodies against Annexin A2, actin and ATP-synthase, ubiquitin-C-terminal hydrolase L1, and CD40 antibodies were detected across both pediatric and adult INS patients in a variable percentage of INS patients highlighting the complexity of this pathology. Recently, the presence of anti-nephrin antibodies in post-transplant recurrent focal segmental glomerulosclerosis patients (7), as well as in the blood and kidney biopsies of patients with minimal change disease (8).

As shown, INS displays a multifactorial and complex pathogenesis, where immunological, genetic, and epigenetic factors are involved. There is therefore an urgent medical need to find early biomarkers to allow for a precise selection and duration of the treatment, avoiding unnecessary severe side effects, and to characterize sub-cohorts for clinical studies. Biofluid secretome can harbor promising disease biomarkers (9). These biomarkers will also favor the understanding of the pathogenesis, allowing for an alternative classification and stratification of the patients.

The PRECISE proposal aims to address unmet needs in INS children, searching for biomarkers/indicators/predictors of this rare kidney primary disease. In this context, we hypothesize

Dipartimento Area Materno - Infatile

SC NEFROLOGIA E DIALISI PEDIATRICA – TRAPIANTI DI RENE – Direttore: [name]

[contact]

email: [contact]

that biomarkers obtained from liquid biopsies (blood and urine) will improve the stratification and prognosis of INS patients, allowing for accurate tailoring of treatments. As the pathogenesis of the disease is multifactorial, an integrated cellular and secretome multi-omics approach will allow for the identification of biomarkers across multiple levels, to be then validated in the routine clinical setting.

7. Objectives

The **PRIMARY OBJECTIVE** of the **PRECISE** study is the generation of a predictive model to differentiate children with SRNS or SDNS from patients with IRNS at the onset through the integration of -omics, genetic, and clinical data (biomarker signature).

The following **4 SECONDARY OBJECTIVES** will be pursued in the study:

1. Definition of the genetic/epigenetic modifications participating in the pathogenesis of INS.
2. Evaluation of adaptive immune system alterations in INS children.
3. Identification of specific protein patterns in serum and urine in different INS subtypes.
4. Description of the molecular characteristics in healthy children.

8. Methods

8.1 Study design

Open, multicenter, non-pharmacological observational study.

[figure not shown]
Dipartimento Area Materno - Infatile

SC NEFROLOGIA E DIALISI PEDIATRICA – TRAPIANTI DI RENE – Direttore: [name]

[contact]

email: [contact]

Pediatric Idiopathic nephrotic syndrome

The PRECISE study is an open, multicenter, non-pharmacological biological study. The study will recruit a total of 310 INS patients and 40 controls. In details, the study will recruit 110 treatment-naïve childhood INS patients as a discover cohort, who will be followed for 12 months. At enrolment urine and blood samples will be collected as for normal clinical practice for the planned analysis. At the 12-month follow-up, patients will be classified according to international guidelines as steroid-dependent (SDNS)/frequent relapsing (FRNS) and infrequent relapsing nephrotic

Dipartimento Area Materno - Infatile

SC NEFROLOGIA E DIALISI PEDIATRICA – TRAPIANTI DI RENE – Direttore: [name]

[contact]

email: [contact]

syndrome (IRNS) (10). Additional assessments and biological samples will be performed according to the study flowchart and as described in the study procedure chapter. A homogeneous control group (n=40) by age of children undergoing sampling for minor urological surgical correction procedures will be also enrolled. In the validation phase, biological samples from an independent group of prevalent INS (200 cases) cases will be collected.

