9.1 STUDY POPULATION (incident patients)

Inclusion criteria

1. Clinical diagnosis of idiopathic nephrotic syndrome (nephrotic range proteinuria uPr/uCr ratio > 2mg/mg, hypoalbuminemia < 3.0 g/dl, oedema);
2. No previous treatment for INS
3. age between 1 and 18 years at onset
4. signed informed consensus

Exclusion criteria

1. Congenital or infantile nephrotic syndrome (age < 1 year old); secondary nephrotic syndrome; glomerulonephritis; autoimmune diseases; vasculitis.
2. Absence of signed informed consensus
3. previous treatments with prednisone or prednisolone for INS

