9.3 VALIDATION COHORT

Dipartimento Area Materno - Infatile

SC NEFROLOGIA E DIALISI PEDIATRICA – TRAPIANTI DI RENE – Direttore: [name]

[contact]

email: [contact]

Inclusion criteria

1. Previous clinical diagnosis of idiopathic nephrotic syndrome (nephrotic range proteinuria uPr/uCr ratio > 2mg/mg, hypoalbuminemia < 3.0 g/dl, oedema);
2. age between 1 and 18 years at onset
3. signed informed consensus

Exclusion criteria

1. Congenital or infantile nephrotic syndrome (age < 1 year old); secondary nephrotic syndrome; glomerulonephritis; autoimmune diseases; vasculitis.
2. Absence of signed informed consensus

10. Study procedure

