10.1 Study visits

Population 1 (main population incident INS):

At the enrollment visit, prior informed consent the following assessments will be performed: physical examination, assessment of oedema, measurement of vital signs, blood and urine samples collection (see A. Schedule of assessments for more details). Afterwards, patients will be assessed at 6 weeks, 6 months and 12 months according to A. Following the international guidelines, at the 12 months visit patients will be clinically classified as SRNS, SDNS, or IRNS according to their medical history. Schedule of assessments: main population (incident INS).

Patient will come back to the center in case of relapse (see definitions) to perform the ‘first relapse visit’ according to A. Schedule of assessments: main population (incident INS).

Population 2 (control group):

This population will perform after informed consent only the enrollment visit, according to B. Schedule of assessments: control group.

Population 3 (validation cohort):

Patient will be enrolled after informed consent at relapse (enrolment visit). During this visit, a physical examination, assessment of oedema, measurement of vital signs and collection of blood and urine samples will be performed according to C. Schedule of assessments: validation cohort. At the remission (see definitions), patients will come back to the center to perform the remission visit according to C. Schedule of assessments: validation cohort.

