10.3 Demographic data

Demographic data (age, sex, and ethnicity, appearance age) and response to therapy will be collected for all participants during the enrollment visit.

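### The 200 prevalent children sampled at relapse and remission cannot by themselves validate onset prediction for time-varying markers, and Schedule C names neither treatment at sampling nor genetic blood

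*Protocol*

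**What the plan says.** **Target.** Section 7 sets the primary objective as a predictive model to "differentiate children with SRNS or SDNS from patients with IRNS at the onset".

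**Discovery cohort.** Section 9.1 requires "No previous treatment for INS" in the 110 incident children. They are sampled at onset and, under section 10.1, "at the 12 months visit patients will be clinically classified as SRNS, SDNS, or IRNS according to their medical history".

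**Validation cohort.** Section 8.1: "In the validation phase, biological samples from an independent group of prevalent INS (200 cases) cases will be collected". Section 9.3 asks for "Previous clinical diagnosis of idiopathic nephrotic syndrome", an age range at onset and consent. Neither its inclusion nor its exclusion list mentions past or current treatment. Section 10.1 on timing: "Patient will be enrolled after informed consent at relapse (enrolment visit". A second visit follows at remission. Schedule C has these two columns only.

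**Analysis.** Section 15.1 says the selected features will be examined in public data and afterwards in a bigger consortium cohort, which it does not identify. Sections 7, 8.2, 8.3, 13 and 15.2 do not name the 200.

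**Treatment data.** Section 10.3 says "response to therapy will be collected for all participants during the enrollment visit". The history items listed in 10.4 do not include medication. Schedule C ticks medical history at enrolment only. Section 17 undertakes to adjust for confounders where this is possible.

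**Genetic blood.** Section 10.9 provides for genetic and epigenetic blood from every nephrotic syndrome patient. Schedule A has a row for it; Schedule C does not.

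**The concern.** A reader who meets a validation phase after a model-building phase will take its result as confirming or refuting the model. Here the two cohorts differ in the two respects most likely to move the markers: treatment exposure and stage of disease. The discovery samples are untreated and taken at onset. The validation samples come from children with an earlier diagnosis, possibly treated, in relapse or remission.

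If children with a worse course are treated differently, treatment is associated with the class being predicted. A marker that merely responds to treatment could then appear to replicate, and a genuine onset marker could appear to fail. Adjustment would help only if treatment at each sampling had been recorded, and that is harder to recover after collection.

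Separately, if Schedule C is followed as written, no genetic blood is drawn from the 200. The one component that prevalent cases could check without this difficulty would then go untested.

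**Working it through.** **1. The protocol's own total.** Section 8.1 gives 310 patients: 110 + 200 = 310, which agrees. Children with an untreated onset sample: 110/310 = 35.5%. Children without one: 200/310 = 64.5%. Ratio of the cohorts: 200/110 = 1.8, so it is not evident that the 200 are the much bigger cohort of section 15.1.

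**2. The cohorts side by side.**

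| | Discovery (110) | Validation (200) |
|---|---|---|
| Disease state at entry | Onset (Schedule A) | Relapse (10.1, Schedule C) |
| Prior treatment | Not allowed (9.1) | No criterion (9.3) |
| Other samples | 6 weeks, 6 and 12 months, first relapse; set varies by visit | Remission |
| Classification step | At 12 months (10.1) | None stated |
| Genetic blood row | Yes | No, despite 10.9 |
| Treatment at sampling | Untreated at entry by criterion | Not a named item at either visit |

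None of the 200 supplies an untreated onset measurement. Germline variants are unaffected, because they do not change with treatment or stage.

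**3. How far treatment could distort a result (illustration only).** The protocol gives no treatment shares or effects, so every input here is assumed. Let the marker be N(0,1), plus d in SRNS/SDNS, plus δ if treated at sampling. Let the treated shares be p1 in SRNS/SDNS and p0 in IRNS. Without adjustment:

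AUC = p1(1−p0)·Φ((d+δ)/√2) + [p1·p0 + (1−p1)(1−p0)]·Φ(d/√2) + (1−p1)p0·Φ((d−δ)/√2)

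Worked case, no onset signal: d = 0, δ = 1, p1 = 0.8, p0 = 0.2. Then 0.64 × 0.760 + 0.32 × 0.500 + 0.04 × 0.240 = 0.486 + 0.160 + 0.010 = 0.656.

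Worked case, true onset AUC 0.70 (d = 0.742) with an opposite shift: δ = −1, same shares. Then 0.64 × 0.428 + 0.32 × 0.700 + 0.04 × 0.891 = 0.274 + 0.224 + 0.036 = 0.533 (from unrounded terms).

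| Treated shares p1 / p0 | No onset signal: δ = 0.5 / 1.0 | Onset AUC 0.70: δ = −0.5 / −1.0 |
|---|---|---|
| 50% / 50% | 0.500 / 0.500 | 0.694 / 0.680 |
| 60% / 40% | 0.528 / 0.552 | 0.670 / 0.632 |
| 70% / 30% | 0.555 / 0.604 | 0.645 / 0.584 |
| 80% / 20% | 0.583 / 0.656 | 0.620 / 0.533 |

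The distortion ranges from none to large depending on how unequal treatment is between classes, and the study as scheduled names no item that would show this at each sampling.

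**The case against.** **The protocol does not claim in terms that the 200 validate onset prediction.** The objective is to generate a model, and the primary endpoint in 8.2 describes signatures without an onset limit. A reader might infer that the protocol says nothing anywhere about the cohort's purpose. That goes too far: the 8.1 figure is not shown, so only the supplied text can be called silent. What stands is that this text labels the cohort as validation without saying of what.

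**The cohort has real uses.** Schedule A collects mononuclear cells, urine and serum at first relapse, so a relapse-to-relapse comparison with the 200 is possible, and germline variants can be checked in prevalent cases. A reader might infer that the 200 have no validation value; the documents do not support that. But no such comparison is stated, and it would test replication at relapse, not prediction at onset.

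**Some of this belongs in an SAP or eCRF.** The method of adjustment does. The list in 10.4 need not be exhaustive, and section 12 draws clinical data from each visit's medical records, so treatment may be obtainable. Yet an SAP cannot create onset samples or guarantee adjustment for something not recorded. Eligibility, visits and the purpose of a cohort are protocol matters.

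**The study is a descriptive pilot (sections 13 and 17).** This limits the consequences. It does not change how a validation result will be read.

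**The AUC figures are assumed throughout.** Correct. The extremes need 80% against 20% treated and a shift of one standard deviation.

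**Conclusion.** The point holds for time-varying markers: the 200 cannot by themselves validate prediction at onset, because none has an untreated onset sample and treatment is unrestricted. It does not hold for germline variants, although Schedule C as written supplies no blood for them. Treatment at sampling is not a named item at either Schedule C visit, so the adjustment promised in section 17 may not be possible. This should be fixed; it does not stop the study from running.

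These conclusions rest on the protocol's text alone. The AUC figures rest on assumed treatment shares and effects and are not an estimate of the bias.

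A reader might also infer that entry at relapse keeps out SRNS children who never remitted. The documents do not support that conclusion, because section 10.1 relies on definitions of relapse and remission that are not in the supplied text.

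**What to change.** 1. In 8.1 and 15.1, state that the 200 test whether the discovery signature is associated with known course in established disease, with treatment at sampling taken into account. State that their relapse samples are compared with the discovery cohort's first-relapse samples already in Schedule A. State that onset prediction is assessed only by resampling within the 110, unless other incident onset data are named. Say whether the 200 are the bigger cohort of 15.1.
2. Add current treatment at sampling as a recorded item at both Schedule C visits, taken from the visit medical records that section 12 already uses.
3. Reconcile Schedule C with 10.9 on genetic and epigenetic blood.

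The cost is wording in two sections, one eCRF item at two visits and one schedule row to reconcile. No sample size changes. The downside is a narrower validation claim.

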8.2. Primary endpoint

To describe different molecular signatures (characteristics), predictive of the progression of INS, which would be able to discriminate among SRNS/SDNS and IRNS groups, based on genetic/epigenetic background, immune status, and vesicular proteome/transcriptomic profile.

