15.1 Primary endpoints: analysis

Statistical analysis using linear mixed effect models will ensure that data from the same individuals over time are properly considered. Network-based analysis using a linear mixed effect model LASSO implementation will allow us to identify key features associated with various clinical endpoints. To identify subsets of features, across all OMICs, associated with disease progression and treatment response, we will use a genetic algorithm-based feature selection approach. Unlike LASSO, this approach can identify non-linear relationships between features and can be linked to almost any predictive modeling approach. The feature subsets will further be evaluated in already available public domain data and then applied to a much larger cohort within the PRECISE consortium.

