1. Due to the nature of the pathology (rare disease), one of the risks could be not reaching the number of recruited patients (annual incidence of 2-7/100,000 children). Our contingency plan will be the integration of additional ERKnet and ESCAPE Network centers through an addendum to the protocol.
2. The other limitation could be the absence of sample stability. Our contingency plan will be to define specific isolation workflow protocols, centralize the biobanking system, and perform sample stability tests for the different applications.
3. Another problem could be a difficult blood draw based on the age of the new-onset children recruited in the study. We will exclude Infantile N from the study to overcome this problem.

From the statistical side, all the data will be extensively scrutinized to ensure that misreporting is minimized. Potential confounders will be identified and assessed routinely throughout the analysis. Where possible, confounding factors will be adjusted for in the analysis. Where < 10% of missing data are present in a variable we will aim to impute missing data from other available data sources using a random Forest regression or classification approach. Variables with >20% missing values within a group will be kept aside and used only for descriptive quantitative evaluations. Statistical analysis using linear mixed effect models will ensure that data from the same individuals over time are properly considered.

18. Other aspects

The study will be conducted by the Standards of Good Clinical Practice, the ethical principles deriving from the Declaration of Helsinki.

The study and the related documentation will be presented to the competent Ethics Committee of each center. The study will begin only after receiving the authorizations requested according to the institution's internal procedures.

The Ethics Committee must also approve any changes to the protocol and advertising used to recruit subjects for the study, according to local regulations.

18.1 Informative note to subjects and consensus module to personal data treatment.

The investigators have the responsibility to obtain a signed informed consent by parents or legal

Dipartimento Area Materno - Infatile

SC NEFROLOGIA E DIALISI PEDIATRICA – TRAPIANTI DI RENE – Direttore: [name]

[contact]

email: [contact]

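### The primary objective includes clinical data in the predictive model, the primary endpoint omits them, and no assessment of value beyond onset clinical data is planned

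*Protocol*

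**What the plan says.** Four parts of the protocol bear on the content of the primary model.

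- **Section 7 (primary objective):** a predictive model that distinguishes SRNS or SDNS from IRNS at onset, built "through the integration of -omics, genetic, and clinical data (biomarker signature").
- **Section 8.2 (primary endpoint):** "To describe different molecular signatures (characteristics), predictive of the progression of INS", able to separate the same groups, "based on genetic/epigenetic background, immune status, and vesicular proteome/transcriptomic profile".
- **Section 15.1 (primary analysis):** a mixed-model LASSO step that "will allow us to identify key features associated with various clinical endpoints", then a genetic-algorithm selection step whose purpose is given as "To identify subsets of features, across all OMICs, associated with disease progression and treatment response".
- **Section 17 (limitations):** "Where possible, confounding factors will be adjusted for in the analysis". The confounders are not named.

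Section 6 gives the hypothesis that "biomarkers obtained from liquid biopsies (blood and urine) will improve the stratification and prognosis of INS patients". On data collection, section 10.3 says "Demographic data (age, sex, and ethnicity, appearance age) and response to therapy will be collected for all participants during the enrollment visit". Schedule A adds albumin and the urine protein/creatinine ratio at enrolment. Section 13 calls the study descriptive and exploratory, with no inference on the primary endpoint.

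**The concern.** Objective, endpoint and analysis should describe one model with one set of candidate predictors and one target. Here the clinical layer is present in the objective, missing from the endpoint, and not named among the candidates in the selection step. The target also loosens, from a defined 12-month class to progression, treatment response and an unspecified set of clinical endpoints.

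Two things are at stake. First, a molecular signature that mostly re-expresses age or severity at onset would satisfy section 8.2 as worded, yet tell a clinician nothing beyond the enrolment visit. The hypothesis that biomarkers will improve stratification invites the question of what they improve on, and the protocol plans no analysis that answers it. Second, without a single named target in 15.1, a reader of the final report cannot tell which result was meant to be primary.

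**Working it through.** **Step 1: the texts side by side.**

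| Section | Candidate predictors | Target |
|---|---|---|
| 7 | omics, genetic, clinical | SRNS or SDNS versus IRNS |
| 8.2 | genetic/epigenetic, immune, vesicular proteome/transcriptome | SRNS/SDNS versus IRNS |
| 15.1, LASSO step | features, type not stated | several clinical endpoints, not listed |
| 15.1, selection step | omics features | progression and treatment response |

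The clinical input is the one that drops out between 7 and 8.2. In 15.1 the word clinical appears only on the outcome side, and the SRNS/SDNS versus IRNS class is not named.

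**Step 2: is added value assessed elsewhere?** The only other route for clinical variables is the confounder adjustment in section 17. An adjusted association says whether a feature is related to outcome given the covariates. It does not say how much better a combined model predicts than a clinical one. No section names a clinical-only reference model.

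**Step 3: are the data there?** Yes. Age, sex, albumin and urine protein/creatinine ratio are all recorded at enrolment in the incident children (section 10.3 and Schedule A).

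**Step 4: how precise would the comparison be?** The protocol gives no figure to reproduce: no class split, no AUC, no precision target. The following inputs are therefore assumptions: 50 versus 60 children out of 110, combined AUC 0.75, clinical-only AUC 0.69, and correlation r between the two AUC estimates of 0.5 to 0.8.

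Standard variance formula, with P1 = A/(2−A) and P2 = 2A²/(1+A):

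Var(A) = [A(1−A) + (n1−1)(P1−A²) + (n2−1)(P2−A²)] / (n1·n2)

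- A = 0.75: P1 = 0.6000, P2 = 0.6429, A² = 0.5625. Var = (0.1875 + 49×0.0375 + 59×0.0804)/3000 = 0.002255. SE = 0.0475, 95% half-width 1.96×0.0475 = 0.093.
- A = 0.69: P1 = 0.5267, P2 = 0.5634, A² = 0.4761. Var = (0.2139 + 49×0.0506 + 59×0.0873)/3000 = 0.002616. SE = 0.0511, half-width 0.100.

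Paired difference: Var(d) = 0.002255 + 0.002616 − 2r×0.0475×0.0511.

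| r | SE of difference | 95% half-width |
|---|---|---|
| 0.5 | 0.0494 | 0.097 |
| 0.7 | 0.0383 | 0.075 |
| 0.8 | 0.0314 | 0.062 |

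The assumed gain is 0.75 − 0.69 = 0.06, so the interval includes zero in all three rows.

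**Step 5: sensitivity to the split.** At AUC 0.75 the single-model half-width is 0.099 for 40/70, 0.106 for 33/77 and 0.131 for 20/90. For 20/90 the two variances are 0.004473 and 0.004971 (SE 0.0669 and 0.0705). The same difference formula then gives half-widths of 0.135 at r = 0.5 and 0.085 at r = 0.8. Less balanced classes make the comparison less precise.

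**The case against.** The strongest reply is that only the mismatch between 7 and 8.2 is firm. The LASSO step does not restrict feature type, section 17 provides for confounders, and details of a comparator model commonly sit in an SAP, which is not shown. Sections 7 and 8.2 agree on the target, and progression and treatment response in 15.1 can be read as a loose paraphrase of the class. The study calls itself descriptive and a pilot, and Step 4 shows that a gain in AUC could not be resolved sharply.

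Much of this stands, and it rules out three stronger readings:

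- **That clinical variables are excluded from the primary analysis.** A reader might infer this from 8.2 and the selection step, but the open LASSO wording and section 17 do not support it.
- **That the trial cannot show added value.** The enrolment data are collected in the same children, so the comparison remains possible. It is simply not planned in this document.
- **That several targets inflate a false-positive rate.** Section 13 disclaims inference on the primary endpoint, and 15.1 sets no significance test for it and lists no fixed number of targets. No error rate can be computed.

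The objection does not remove the conflict itself. An SAP must choose between a signature with clinical data and one without, and it cannot satisfy both 7 and 8.2. A descriptive study still has to define its predictors and target. The absence of the serum proteome from 8.2 carries little weight, since it has its own place as secondary endpoint 8.

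**Conclusion.** The concern is upheld as an inconsistency that should be corrected. The objective includes clinical data and the endpoint does not. The selection step names omics features only and does not name the SRNS/SDNS versus IRNS class. As written, the protocol plans no assessment of value beyond onset clinical data, and confounder adjustment where possible does not supply one.

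The textual finding rests on no assumption. The size of the precision problem does: with 50 versus 60 children and AUCs of 0.75 and 0.69, the 95% half-width of the AUC difference is about 0.06 to 0.10 for correlations of 0.8 to 0.5, and wider if the classes are less balanced. That is a reason to report the gain descriptively. It does not justify leaving it out, and no change in sample size follows, because section 13 sets 110 on feasibility.

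**What to change.** Align sections 8.2 and 15.1 with section 7:

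1. Name SRNS/SDNS versus IRNS at 12 months as the single primary target in 15.1. Label any analysis of progression, treatment response or other endpoints as secondary or exploratory.
2. Include a small fixed set of enrolment variables already in Schedule A in the primary model, for example age, sex, urine protein/creatinine ratio and albumin, and say so in 8.2. Use only values known at onset.
3. Report the clinical-only model beside the combined model, both from the same resampling folds, with the AUC difference and its confidence interval as a descriptive estimate. Do not make that difference the sole primary result.

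The cost is protocol and SAP wording plus one extra model, with no new visits, samples or patients. The drawback is that the gain will look smaller than a stand-alone molecular AUC and will be imprecise at 110 children. The protocol should state this in advance, with any assumed class split and AUCs labelled as assumptions.
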